**Half-face Evaluation of Melasma Area Severity Index (MASI) Score**

At all visits, (baseline, weeks 4, 8 and 12), the Investigator will assign a grade for the left and right facial sides, for each of the below units, for the variable A (percentage of each area involved), D (darkness of pigment) and P (pattern of involvement), as described in detail below.

Calculations will be conducted by the sponsor upon receipt of the completed CRFs.

**3 variables are assessed for each half- facial unit:**

- Total Area Involved (**A**)
- Darkness of pigment (**D**)
- Homogeneity (**H**)

**Variable Definitions:**

***A = A numerical value is assigned for the corresponding percentage of the total area of the facial segment being assessed.***

This value represents ONLY the percent of the area involved, not the pattern or darkness of the pigment.

- 0**= No involvement
- 1**= <10% involvement
- 2**= 10-29% involvement
- 3**= 30-49% involvement
- 4**= 50-69% involvement
- 5**= 70-89% involvement
- 6**= 90-100% involvement

**D = Darkness of the pigment compared to adjacent normal pigment.**

- 0= Normal skin color
- 1= Slightly darker than normal color
- 2 = Mild hyperpigmentation
- 3= Moderate hyperpigmentation, clearly and distinctly darker than normal pigment
- 4 = Severe hyperpigmentation, virtually black pigment

**H = The homogeneity of the pigmentation will be assessed using the below scale:**

- 0= Normal skin color without evidence of hyperpigmentation
- 1= Specks of involvement
- 2 = Small patchy areas of involvement < 1.5 cm diameter
- 3 = Patches of involvement > 2 cm diameter
- 4 = Uniform skin involvement without any clear areas

Calculation of the half-face MASI score:

To calculate the half-face MASI score, the sum of the severity grade for darkness (D) and homogeneity (H) is multiplied by the numerical value of the areas (A) involved and by the percentages of the four facial areas (10-30%).

Total Half-Face MASI score:

Half Forehead  $0.15(D+H)A$  + One Malar Side  $0.3(D+H)A$  + Half Chin  $0.05(D+H)A$

**Investigator's Global Improvement Assessment- Overall Hyperpigmentation:**

The expert grader will also score an Investigator's Global Improvement Assessment for Overall Hyperpigmentation on the left and right facial sides at all follow-up visits (weeks 4, 8, and 12).

- 0=No change or worsening
- 1=Mild improvement (~25% overall improvement)
- 2=Moderate improvement (~50% overall improvement)
- 3=Marked improvement (~75% overall improvement)
- 4=Complete clearing/Dramatic improvement (~95%+ overall improvement)

**6.2 Investigator's Tolerability Assessment**

Tolerability of the test products will be assessed through the capture of adverse events reported throughout the study period. Any adverse event(s) experienced by the subject

during the study period, whether related to the treatment or not, will be recorded in the “Case Report Form.”

### **6.3 Subject MELASQOL Assessment**

Subjects will complete the MELASQOL assessment regarding their full face at the baseline visit and their left and right facial sides at week 12. The MELASQOL is a validated assessment to help measure the emotional and psychological impact of melasma (3). This questionnaire is found in [REDACTED]

### **6.4 Subject Self-Assessment Questionnaires**

Subjects will complete a Sponsor-provided self-assessment questionnaire at follow-up visits at weeks 4, 8, and 12. The assessment consists in a personal and subjective evaluation of their facial skin quality on the left and right side during and after the treatment by the subject. In addition, the assessment serves to evaluate the self-perceived cosmetic efficacy of the treatment and the product attributes. This questionnaire is found in [REDACTED]

### **6.5 Imaging Procedures**

Photographs will be taken at all visits utilizing standardized conditions for all subjects. The skin must be cleansed prior to photography to remove any makeup, including foundation makeup, lipstick/gloss and eye shadow. The settings for the exposure, lighting, flash, and focal length will be maintained constant over the course of the study.

Ensure that subjects jewelry is removed from ears/neck and hair is pushed back away from the face, ensuring that no stray hairs are in the facial area.

Subjects will be photographed using an appropriate clinical digital photography system [REDACTED] at highest resolution in a consistent position. Importantly, the photography should be taken to enable comparison of baseline photos with later photos taken at the end of the treatment period. For instance, if available, the overlay function must be used. As each photograph is being taken, it should be viewed to ensure that it is in focus and is similar to its baseline counterpart in all technical aspects, including lighting, distance and angle. In addition, the face should be captured in neutral facial expressions and neutral angles (e.g., avoiding hypo- or hyperextension of the neck).

Photos using the [REDACTED] will be taken from three angles to enable the improvement to be clearly noticed: full frontal (0°) and at profile from the left (45°) and from the right side (45°). Photos will be taken at controlled distances under standard room lighting. Cross-polarized, parallel- polarized and visible light images will be acquired along with both blue fluorescence and ultraviolet fluorescence images. During the photography, the subjects will be asked to keep their eyes closed.

### **6.6 Mexameter Instrumentation Procedures**

Two target hyperpigmented lesions will be selected from the left (1) and the right (2) malar facial areas and measured by the mexameter, and instrument that measures

melanin content. Measurements at subsequent visits must be taken from the same target lesion locations as at the baseline visit within each subject.

One target “normal” measurement will also be taken from an unaffected skin area on the face representing normal skin. The values from the target hyperpigmented lesions will be compared to the normal lesion value.

## **7.0 STATISTICS**

Statistical analyses will be conducted by the sponsor on an intent-to-treat basis (ex: all enrolled subjects, with at least one follow-up visit, will be included in the analysis).

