## 2.0 STUDY OBJECTIVE

The objective of this study is to evaluate the efficacy and tolerability of SkinMedica's cosmetic topical brightener versus 4% hydroquinone in the improvement of the appearance of moderate facial melasma over the course of 12 weeks.

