#### **4.4 Treatment Group Randomization**

Subjects will be randomized in a 1:1 fashion to receive treatment with SkinMedica's cosmetic topical brightener or 4% hydroquinone. A randomization table will be provided by the sponsor and used to determine which facial side will be treated with Test Product A (cosmetic topical serum "Lytera 2.0") and Test Product B (4% hydroquinone) for each subject.

- Randomization and distribution of study products by the Unblinded study staff

[REDACTED]

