#### **Melasma Severity Rating Scale:**

At the screening/baseline visit and the end of treatment visit (week 12), the Investigator will assess the subject's facial skin for the severity of symmetrical facial melasma using the following Melasma Severity Rating Scale on the left and right facial sides. Subjects must present with a score of 2 for the left and the right facial sides to be enrolled into the study.

Score	Hyperpigmentation Status
0	Cleared: color of melasma lesions approximately equivalent to surrounding normal skin or with minimal residual hyperpigmentation
1	Mild: color slightly darker than the surrounding normal skin
2	Moderate: color moderately darker than the surrounding normal skin
3	Severe: color markedly darker than the surrounding normal skin

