**Overall Hyperpigmentation Scale:**

At all visits (baseline, weeks 4, 8 and 12), the Investigator will globally assess the subject's left and right facial sides for overall hyperpigmentation using the following ten point scale (0 – 9):

None (Score of 0)	Skin is normal in color with no evidence of hyperpigmentation
Mild (Score of 1, 2 or 3)	Several brown spots with increased pigmentation; they are small in size and slightly darker than surrounding skin
Moderate (Score of 4, 5 or 6)	Many brown spots with increased pigmentation; they are medium in size and much darker than surrounding skin
Severe (Score of 7, 8 or 9)	Many large brown spots with increased pigmentation; they are large in size and markedly darker than surrounding skin

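### Section 7.0 names no primary endpoint, visit or A-B contrast, although at least 11 per-side comparisons are collected without ranking

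*Combined protocol and SAP*

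**What the plan says.** Section 7.0 reads "Statistical analyses will be conducted by the sponsor on an intent-to-treat basis", and explains that basis by saying that "all enrolled subjects, with at least one follow-up visit, will be included in the analysis". It says nothing about endpoint, visit, contrast, test, significance level, multiplicity or missing data. It carries no redaction mark and points to no appendix or separate SAP. The wording is the same in the original protocol and in Amendment 1.

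The objective in Section 2.0 is comparative, Product A "versus 4% hydroquinone in the improvement of the appearance of moderate facial melasma over the course of 12 weeks", but names no measure and no single time point. Section 4.4 makes the design a within-subject one: "A randomization table will be provided by the sponsor and used to determine which facial side will be treated with Test Product A".

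Section 6 then lists outcomes scored for each side of the face:

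- Melasma Severity Rating Scale: "At the screening/baseline visit and the end of treatment visit (week 12), the Investigator will assess".
- Overall Hyperpigmentation Scale: "At all visits (baseline, weeks 4, 8 and 12), the Investigator will globally assess".
- Half-face MASI: "At all visits, (baseline, weeks 4, 8 and 12), the Investigator will assign a grade for the left and right facial sides".
- Investigator's Global Improvement Assessment: both sides at Weeks 4, 8 and 12, with no baseline score.
- MELASQOL (Section 6.3, Amendment 1): whole face at baseline, each side at Week 12.

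The self-assessment questionnaire (6.4) and the Mexameter (6.6) also yield left and right values.

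**The concern.** A comparative trial needs its main comparison fixed before anyone can see which one came out best. Here the reader cannot tell whether success means a difference in MASI, in the hyperpigmentation scale, in global improvement or in quality of life, nor whether it is judged at Week 4, 8 or 12. Each choice is defensible on its own, and each gives a valid paired contrast. The difficulty is that all of them remain open until the data are in. A result headlined from such a set has a false-positive risk above its nominal level, and adjusting over the whole set afterwards is expensive with 20 subjects.

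A smaller gap goes with it. The analysis set keeps a subject who attended only one follow-up visit, but nothing says how that subject enters a Week 12 comparison.

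**Working it through.** **Inputs.** From the documents: 20 subjects (Synopsis), both products on each face, follow-up at Weeks 4, 8 and 12. The documents give no significance level, power, SD or correlation, so there is no planned figure to reproduce. Assumed here: two-sided 0.05 per test, paired t tests with ordinal scores treated as continuous, and equal correlation of 0.5 to 0.9 between the paired differences.

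**Step 1: count the comparisons.**

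| Outcome | Post-baseline visits | Comparisons |
|---|---|---|
| Melasma Severity Rating Scale | 12 | 1 |
| Overall Hyperpigmentation Scale | 4, 8, 12 | 3 |
| Half-face MASI | 4, 8, 12 | 3 |
| Global Improvement | 4, 8, 12 | 3 |
| MELASQOL | 12 | 1 |

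The sum is 1 + 3 + 3 + 3 + 1 = 11, of which 5 are at Week 12. This is a floor. The questionnaire, taken as one item per visit, makes 14. The Mexameter, whose visits are not listed (1 to 3 assumed), makes 15 to 17.

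**Step 2: chance of at least one false positive.** Under independence, 1 - 0.95^11 = 43.1%. That is an implausible upper bound, because four of the five scales are investigator or grader ratings of the same pigmentation. Simulation of 100,000 trials with 20 subjects and no true difference gives:

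| Correlation | 11 tests, either direction | 11 tests, favouring A only | 5 Week 12 tests, either direction |
|---|---|---|---|
| 0.5 | 31% | 16% | 19% |
| 0.7 | 23% | 12% | 15% |
| 0.8 | 19% | 9% | 13% |
| 0.9 | 14% | 7% | 10% |

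One named contrast gives 5% in either direction and 2.5% in favour of A.

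**Step 3: what adjusting over everything would cost.** With 20 pairs the critical value is t(0.975, 19) = 2.093. By the noncentral t distribution with noncentrality d x sqrt(20), power reaches 80% at d = 0.66 SD of the paired difference. With Bonferroni over 11, alpha is 0.05/11 = 0.00455 and the critical value 3.216. The detectable effect rises to 0.92 SD, and power at 0.66 SD falls from 80% to 42%.

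**Step 4: missing Week 12 pairs.** The 95% CI half-width, in SD units, is t(0.975, k-1)/sqrt(k) for k complete pairs: 0.468 for 20, 0.482 for 19, 0.497 for 18 and 0.533 for 16. The loss of precision is modest. These figures do not measure bias, which depends on why pairs are missing and on the rule used.

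**Step 5: where baseline adjustment is possible.** Severity must be 2 on both sides at entry, so its baseline side difference is always zero. Global Improvement has no baseline. The MELASQOL baseline is whole-face. Only MASI, Overall Hyperpigmentation and the Mexameter have a per-side baseline that can vary. For such an outcome, 20,000 simulated trials per case give a mean half-width of 0.462 SD unadjusted. Adjusted for baseline difference and treated side, it is 0.479, 0.457 or 0.415 SD at an assumed baseline-change correlation of 0, -0.3 or -0.5. Adjustment therefore costs about 0.02 SD at worst in these cases.

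**The case against.** The strongest reply is that no visible text announces a hypothesis test, a significance level or an intention to headline one result. The error rates are therefore conditional on a use of the data that the plan does not declare. That is correct, and the rates should be quoted with that condition. It is also fair that a sponsor interested only in results favouring its own product faces about half the two-sided rate. The inflation over nominal remains in both cases. Calling the study exploratory does not help, because the stated objective is comparative and no visible text uses that label.

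A primary endpoint may be stated in Section 5 or an appendix, which cannot be seen. If so, a cross-reference in 7.0 would answer the main point.

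Three stronger readings are tempting and are not supported:

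- A reader might infer that the analysts work unblinded, since the sponsor supplies the randomisation table, analyses the data and derives MASI ("Calculations will be conducted by the sponsor upon receipt of the completed CRFs"). No visible text says that analysts see the table before analysis, part of Section 4.4 is redacted, and MASI is fixed arithmetic on the investigator's grades.
- A reader might infer that the MASI weights contradict the text's four areas of 10% to 30%. They agree: forehead 0.15 + 0.15 = 0.30, each malar side 0.30, chin 0.05 + 0.05 = 0.10, total 1.0.
- A reader might take the parallel-arm label in the Synopsis to mean that the comparison is between subjects. Section 4.4 goes on to assign the two products to facial sides within each subject, so the label is loose wording.

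**Conclusion.** The gap is real in the visible text and should be closed. It goes beyond missing detail, because a primary contrast chosen after the sponsor holds the data no longer protects against selection. The size is a false-positive risk of about 14% to 31% (about 7% to 16% favouring Product A, against 2.5%) if any of 11 results may be headlined, compared with 5% for one named contrast. This rests on an assumed two-sided 0.05, correlations of 0.9 to 0.5, paired t tests on ordinal scores and the floor count of 11. Even if attention were confined to Week 12, five candidates leave 10% to 19%. The documents do not show that the analysts are unblinded or that any result has been selected, and the paired comparisons themselves are valid.

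**What to change.** Before the sponsor receives any post-baseline data, amend Section 7.0 as follows.

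1. Name one primary within-subject contrast at one visit, for example the A minus B difference in change from baseline in half-face MASI at Week 12. Another per-side outcome would also serve.
2. If MASI is chosen, first reconcile the third variable, introduced as pattern (P) but defined and used in the formula as homogeneity (H). Also assign a grade to patches between 1.5 and 2 cm, which the homogeneity scale leaves out.
3. Analyse the paired difference with a 95% CI. Adjust for the baseline side-to-side difference only where a varying per-side baseline exists (MASI, Overall Hyperpigmentation, Mexameter). Otherwise use the unadjusted Week 12 paired difference.
4. State how subjects in the analysis set without Week 12 data are handled.
5. Report all other outcomes and visits as secondary estimates with CIs.
6. State that a non-significant difference will not be read as equivalence.

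The cost is protocol wording: no new visits, measurements or subjects. The sponsor gives up a later choice of headline endpoint, and adjustment uses one or two degrees of freedom.

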**STUDY SYNOPSIS**

Protocol Number	SKM16-LYT-MEL Amendment 1
Protocol Title	Randomized, Double-blinded, Split-face Study comparing the Cosmetic Efficacy and Tolerability of Two Topical Products in Subjects with Moderate Facial Melasma
Study Duration	3 months (12 Weeks)
Study Population	20 healthy subjects with Fitzpatrick Skin Types III-VI
Objectives	To evaluate and compare the efficacy and tolerability of two topical products in the improvement of facial melasma
Study Design	Single site, investigator-initiated, double-blinded, parallel arm, randomized treatment, split-face, 12-week study comparing the efficacy and tolerability of SkinMedica's cosmetic topical brightener versus generic hydroquinone 4% topical prescription cream. A total of 20 healthy subjects will be enrolled into this study. Subjects will be screened and randomized at Baseline and will return for visits at Weeks 4, 8 and 12. The test products will be applied only to the affected areas (dark patches) twice a day, morning and evening, every day for 12 weeks. Ancillary products will be provided for basic daily skincare regimen use.
Study Products	
 
• SkinMedica Facial Cleanser
 
• SkinMedica Rejuvenative Moisturizer
 
• SkinMedica Essential Defense Mineral Shield Broad Spectrum SPF 35 Sunscreen
 
• Test Product A (Lytera 2.0)
 
• Test Product B (4% Hydroquinone Topical Cream)
 

Eligibility Criteria	Subjects aged 18+ [REDACTED] with symmetrical moderate facial melasma.

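### The set labelled intent-to-treat requires a follow-up visit and is the only analysis set visible; if used for tolerability, it leaves out subjects who react and leave before Week 4

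*Combined protocol and SAP*

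**What the plan says.** In Amendment 1, Section 7.0 is a single sentence, and the original protocol has the same one. It states that "Statistical analyses will be conducted by the sponsor on an intent-to-treat basis" and then, in a bracket opened by the abbreviation 'ex:', that "all enrolled subjects, with at least one follow-up visit, will be included in the analysis". No other analysis set, missing-data rule or dropout allowance is visible.

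The synopsis fixes the size and timing: "A total of 20 healthy subjects will be enrolled into this study", and subjects "will return for visits at Weeks 4, 8 and 12" after baseline. The global improvement assessment in Section 6.1 also names Weeks 4, 8 and 12 as the follow-up visits. The synopsis makes comparison of both efficacy and tolerability an objective. Section 6.2 gives the tolerability measure: "Tolerability of the test products will be assessed through the capture of adverse events reported throughout the study period". The same section has every adverse event entered on the case report form, with no attendance condition.

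Two outcomes have Week 12 as their only post-baseline time point. For the Melasma Severity Rating Scale: "At the screening/baseline visit and the end of treatment visit (week 12), the Investigator will assess the subject's facial skin". For MELASQOL, Section 6.3 of Amendment 1 has subjects answer "regarding their full face at the baseline visit and their left and right facial sides at week 12".

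**The concern.** An intent-to-treat set does not depend on what happens after randomization, and this one does. For efficacy that is mainly a labelling matter: a subject never seen after baseline has no follow-up grade to contribute, and because each subject carries both products, the two sides leave together.

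Tolerability is different. An adverse event can be known without a follow-up visit, and a reaction is an obvious reason not to come back. Section 13.3 sharpens this. Mild irritation is not counted as an adverse event, whereas persistent moderate-to-severe symptoms, or those with elevation, are. The events that count are plausibly the ones most likely to make someone stop early. If those subjects are outside the set, the reaction rate for the responsible product is too low and the product looks better tolerated than it was. With 20 subjects, each one left out is 1/20 = 5% of the sample.

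There is a smaller, related gap. A subject seen at Week 4 or 8 but not at Week 12 belongs to the set yet has no post-baseline value on the Severity Rating or MELASQOL, and the plan does not say how that is handled.

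**Working it through.** The documents give no power, effect size, dropout or reaction rate, so there is no planned figure to reproduce. The check has two parts: reading the set definition against the schedule, and illustrating the consequence.

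**Inputs from the documents.** N = 20 (synopsis). Follow-up visits at Weeks 4, 8 and 12 (synopsis; Section 6.1). One product per facial side in every subject (Section 4.4). Tolerability measured by adverse events only (Section 6.2).

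**Step 1: who is in the set.** Membership needs at least one follow-up visit, and the first scheduled one is Week 4. A subject who stops earlier and does not return is outside it.

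**Step 2: which set serves tolerability.** Section 7.0 refers to statistical analyses without qualification and no safety set is visible. Either this set applies to tolerability or tolerability has no stated set.

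**Step 3: what exclusion does in a split-face design.** Let r subjects react on one product's side only, none on the other side, and let k of these r leave before Week 4 (assumptions).

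- Rate on the reacting side, all treated subjects: r/20
- Rate in the Section 7.0 set: (r − k)/(20 − k), which is below r/20 whenever k > 0 and r < 20
- Exact two-sided McNemar p with all discordant pairs in one direction: 2 × (1/2)^(r − k), capped at 1

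The plan names no tolerability test. McNemar is used here because it is a natural test for paired yes/no data.

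| r of 20 | k = 0 | k = 1 | k = 2 |
|---|---|---|---|
| 6 | 6/20 = 30.0%, p = 0.031 | 5/19 = 26.3%, p = 0.063 | 4/18 = 22.2%, p = 0.125 |
| 4 | 4/20 = 20.0%, p = 0.125 | 3/19 = 15.8%, p = 0.25 | 2/18 = 11.1%, p = 0.5 |
| 2 | 2/20 = 10.0%, p = 0.5 | 1/19 = 5.3%, p = 1 | 0/18 = 0%, no discordant pairs |

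Both sides share the denominator 20 − k, so nothing is unbalanced there. What is lost is the discordant pair, which carries the information on A versus B. With no reactions on the other side, the difference between products shrinks by the same amount as the rate: in the first row, 30.0 − 22.2 = 7.8 percentage points.

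**Step 4: dependence on who leaves.** The downward direction holds when early leavers are reactors. If one early leaver had not reacted, the first row would give 6/19 = 31.6%, slightly too high.

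**Step 5: how easily it could happen.** If each subject has probability q of leaving before Week 4 with a reaction (assumed), the chance of losing at least one of 20 is 1 − (1 − q)^20: 33% for q = 2%, 64% for 5%, 88% for 10% and 96% for 15%.

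**Step 6: the Week 12 scales.** Membership is met by a Week 4 or Week 8 visit, while the Severity Rating and the side-specific MELASQOL have follow-up values only at Week 12. The number analysed on those two scales can therefore be smaller than the set, by an amount the plan does not require to be reported.

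**The case against.** The strongest reply is that Section 7.0 never says it governs tolerability. Sections 6.2 and 13.1 have all adverse events recorded and assessed for every subject, with no attendance condition, and no formal tolerability test is visible. On that reading adverse events would be listed for all 20 subjects and Section 7.0 would concern the graded outcomes. The abbreviation 'ex:' may also mark the bracket as an example and not a definition. Section 5 is not visible, so an early-termination visit cannot be ruled out. Subjects are asked to report reactions at once (inclusion criterion 6; Section 13.3), so an early reactor might be seen before Week 4.

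All of this stands as a limit on the claim. A reader might infer that early reactors disappear from the trial's safety information. The documents do not support that: the events stay on the case report form, and serious ones are still reported. What is at risk is the comparison, and only if the stated set is used for it. The reply does not remove the problem, because if Section 7.0 does not cover tolerability, a stated objective has no analysis set at all. An early-termination visit would help only if it counted as a follow-up visit.

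A reader might also infer that the rule cannot be carried out for the Week 12 scales. That goes too far. Belonging to an analysis set with a missing value is ordinary; what is absent is a statement of how many have a value and how the rest are handled.

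**Conclusion.** The point holds in a limited form. The intent-to-treat label is wrong on the plan's own words: the set is a modified ITT set. That part needs no assumption unless the bracket is only an example, in which case the set is even less fixed.

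The consequence for tolerability is conditional. It requires that the set be applied to adverse events, that a subject react on one side and leave before Week 4, and that no earlier visit count as follow-up. Under those conditions the reaction rate on that side is understated, tolerability is overstated, and a discordant pair is lost, while the denominators stay equal. The size is wholly assumed. In the illustration with 6 one-sided reactors of 20, two early losses take the rate from 30.0% to 22.2% and the exact p from 0.031 to 0.125.

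This should be corrected because the change is cheap and tolerability is an objective. It does not show that the efficacy contrast is biased by unequal loss between sides, since pairing removes both sides together.

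**What to change.** In Section 7.0:

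- Define a tolerability set of all subjects who applied either product at least once, regardless of follow-up attendance. Analyse adverse events in it by facial side, and record the affected side for each local event.
- Rename the efficacy set 'modified ITT (at least one follow-up visit)' and report the number excluded, with reasons.
- For the Melasma Severity Rating and the side-specific MELASQOL, report the number of subjects with a Week 12 value.

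The cost is a few sentences and one extra table. Side attribution is not mentioned in the visible text, so the case report form may need a field for it. The reported reaction rates may look slightly less favourable.
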